7.6. Subsequent Sessions

Those randomised to the experimental group will be asked to attend for 1 hour per week over the next 3 months at the Skills lab in the Nuffield Orthopaedic Centre for regular simulation training. Motion data may also be recorded during these sessions.

At 3 month follow up, all participants will repeat a simulated arthroscopy assessment lasting about 30-45 mins, similar to that which occurred at baseline, and an in theatre assessment using the same wireless elbow sensors. We aim to coordinate these two events in the same visit.

Junior surgical trainees perform surgery under consultant supervision as part of their training programme. It is during one of these surgical cases, we will gather objective surgical motion data in addition to the usual forms of educational evaluation which take place as part of training.

Participants will attend a consultant supervised knee arthroscopy list at the Nuffield Orthopaedic Centre. The participant and consultant will have the wireless sensors attached to their elbows by adhesive tape or custom sleeves that fit to the elbow. They are securely attached to the surgeon's elbows and do not interfere with thorough surgical scrubbing, nor do they interfere with any theatre equipment. The participant will scrub for the case with the consultant. The consultant will perform the procedure the patient has been admitted for, and once complete, will demonstrate a diagnostic knee arthroscopy (a

keyhole video examination of all the structures within the knee) to the participant as per standard surgical training practise. The consultant will then supervise the participant performing the same procedure as would normally happen during surgical training. They will provide the same support, and interrupt the procedure as they would in any other supervised surgical case if they feel this is necessary.

Participants motion analysis parameters will be compared to those of the supervising consultant, which will act as a bench-marking process to account for the technical differences between cases (e.g. the weight or size of the leg). This wireless motion data will be recorded to assess the elbow sensors' effectiveness at monitoring learning and performance in addition to the usual forms of educational monitoring e.g. Procedure-base assessments and global rating scales.

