3. BACKGROUND AND RATIONALE

The 'Simulation-based Arthroscopic Surgery Programme' MSD-IDREC-C1-2014-152 aims to gather evidence for simulation training during surgical training. On a background of decreasing working time available, less independent operating, and greater public expectations of the medical profession, simulation is seen as an important support to routine surgical training. However, there is little evidence to show it improves surgical performance, and studies not been based on truly objective measurements. The 'Simulation-based Arthroscopic Surgery Programme' has the primary aim of developing evidence-based simulation training by objectively justifying the use of simulation to improve surgical training.

At the Oxford Orthopaedic Simulation and Education Centre (OOSEC) we are investigating new training methods for our future surgeons and using simulators, cadaver specimens and virtual reality models. To ensure evidenced based training we assess the learning and performance of the trainee groups using these various simulators. These groups mainly compromise surgical trainees, consultants and medical students and NHS ethics is not required, however to ensure best practice and as this work can lead to educational publications, we have ethical approval in place from CUREC (Simulation-based Arthroscopic Surgery Programme; MSD-IDREC-2014-152). In addition, and as part of an educational project, we will assess trainees in the real operating theatre as part of their usual training with their consultants, while patients receive their normal treatment.

Motion analysis is a validated objective measure of technical skill used previously in simulated settings: numbers of hand movements and total path length have been shown to decrease with surgeon experience during simulated tasks. Typically, motion analysis involves wired sensors attached to the wrists that are unsuitable for use in theatre as the position interferes with sterile scrubbing. Our group has developed simple elbow-worn wireless motion sensors: besides using these sensors in the simulated setting it is now possible to also use them in the real operating theatre while trainees under go their normal training and assessments.

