7.7. Discontinuation/Withdrawal of Participants from Study

Each participant has the right to withdraw from the study at any time. In addition, the Investigator may discontinue a participant from the study at any time if the Investigator considers it necessary for any reason including:

- Ineligibility (either arising during the study or retrospectively having been overlooked at screening)
- Significant protocol deviation
- Significant non-compliance with treatment regimen or study requirements
- Withdrawal of Consent
- Loss to follow up
- Exclusion from core or higher surgical training programme

The reason for withdrawal, if disclosed, will be recorded in the Case Report Form.

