8. STATISTICS AND ANALYSIS

8.1. Description of Statistical Methods

Motion analysis data from the elbow-worn wireless motion sensors produces similar data to the wired sensors our group has used previously.

Number of movements and path length are common to both devices. Data distributions will be assessed for normality. Previous studies show such data are not normally distributed and we would expect to use non-parametric tests, in this case the Mann-Whitney U test or Kruskal-Wallis test, to compare performance between groups during a given task. Mann-Whitney U tests will also be used within a group to compare performance before and after training on a simulator.

Surgical logbook data will be assessed using descriptive statistics, and motion analysis performance will be reported with reference to surgical experience.

Questionnaire data regarding the trainee and consultant perception of the utility of these sensors will be reported as descriptive statistics.

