9.2. Data Recording and Record Keeping

Anonymised non-personal raw motion data will be uploaded to secure off-site servers using SSL/TLS using strong cipher suites that support perfect forward secrecy. This prevents decoding of captured data, even if the secret long-term key itself is compromised. Every instance has a built in firewall that is configured using a least privilege basis and will only accept https (port 443) connections from the

internet. The data centres are staffed 24x7 by trained security guards and access is authorised strictly on a least privileged basis.

This data will remain anonymised regarding the participant, and will contain no information related to patients. The raw motion data can be queried to generate usable motion analysis metrics (e.g. smoothness, hand movements etc). These are not stored on the server, but generated on request via proprietary algorithms. Pooled anonymised non-personal raw data from participants' motion data is used to generate and refine the algorithms, and as such, as more raw data is acquired by the server, the requested outputs become more accurate. Pooled data cannot be extracted to be attributed to any participant.

Usable output motion analysis metrics will be downloaded from the server and stored locally on an Excel spreadsheet (.xlsx). These data may be opened in other programmes or copied to other formats for certain analyses e.g. SPSS data files (.sav). Where study data are generated in a proprietary file type, these will be transposed to Excel format.

The participants will be identified by a unique study specific number and/or code in any database. The name and any other identifying detail will NOT be included in any study data electronic file. All study data files will be kept on password protected hard-drives. Output study data will be kept for a further 3 years following the completion of the study before being destroyed. Anonymised non-personal raw data from the sensors will contribute to the algorithm on the secure server, but will not be extractable or identifiable to any participant.

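### Completion of the single assessed theatre case is not recorded, so a shortened movement total can read as skill; the GRS rater is unnamed and neither rater nor supervising consultant is masked

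*Combined protocol and SAP*

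**What the plan says.** **Source of the theatre data.** Section 7.6 describes one assessed case per trainee at 3 months: "It is during one of these surgical cases, we will gather objective surgical motion data". The consultant finishes the patient's procedure, demonstrates a diagnostic arthroscopy, then supervises the trainee doing the same, and may "interrupt the procedure as they would in any other supervised surgical case if they feel this is necessary". Both wear sensors. The stated purpose is to judge the sensors' "effectiveness at monitoring learning and performance in addition to the usual forms of educational monitoring".

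**Metrics.** Section 8.1 says "Number of movements and path length are common to both devices" and plans rank tests between groups. Section 3 gives the direction: "numbers of hand movements and total path length have been shown to decrease with surgeon experience during simulated tasks". Section 9.2 also mentions smoothness, which need not fall when a recording is shortened.

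**Adjustment.** The trainee is compared with the supervising consultant, "which will act as a bench-marking process to account for the technical differences between cases"; the example given is the weight or size of the leg.

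**What is recorded when something goes wrong.** Section 7.7 says "The reason for withdrawal, if disclosed, will be recorded in the Case Report Form". That concerns a participant leaving the study, not a theatre case left unfinished.

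**Masking.** Section 7.4 says participants cannot be blinded, and that motion data are coded and analysed blind to allocation. Section 4 lists the GRS in theatre under the primary objective but does not say who scores it.

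**The concern.** A cumulative total means the same thing for two trainees only if both did the whole task. If one stopped early or was taken over, that total is smaller for a reason unrelated to economy of movement, and on these metrics smaller looks better. With one theatre case per trainee, there is no second recording to correct the first.

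The primary objective is whether the sensors are useful in theatre, and section 3 suggests that competence could later be defined from these parameters. A struggling trainee whose shortened case looks efficient counts against the tool for a reason that could have been seen at the time. The comparison of randomised arms, although not the stated primary objective, can also be distorted if incomplete cases are more common in one arm.

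The masking gap is separate. The consultant decides how much help to give, and someone scores the GRS. If either knows the arm, the help or the score could differ by arm. Blind analysis of the motion data cannot undo that.

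**Working it through.** The plan states no power, effect size or interruption rate, so there is no figure of its own to reproduce.

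**1. Possible events, set against the text**

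| Event in the trainee's case | Effect on total | Recording specified? |
|---|---|---|
| Completed without interruption | none | no |
| Pause or correction, then completed | could rise | no |
| Stopped early | falls | no |
| Taken over by the consultant | falls | no |

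**2. What truncation does.** Let T be the total had the case been completed and f the fraction of it recorded. The data hold f × T. A trainee whose complete total would be R times a peer's ranks ahead of that peer when f × R < 1, that is R < 1/f.

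- f = 0.9: R below 1.11
- f = 0.7: R below 1.43
- f = 0.5: R below 2.00
- f = 0.3: R below 3.33

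Late truncation reverses only close pairs; early truncation reverses wide ones. Dividing by the consultant's total C gives f × T / C. If C comes from the consultant's own demonstration, this removes leg size but leaves f.

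**3. Illustration for the motion data.** From the documents: up to 60 trainees allocated 50:50 (section 5), so at most 30 per arm, and the Mann-Whitney test (8.1). Everything else is assumed: log(trainee/consultant total) = 0.4 × skill deficit + noise of SD 0.1; a 0.75 SD training benefit; truncation more likely in weaker trainees (logistic, slope 1.3); 30–70% of the total recorded when truncated, or 60–90% if late. Rates are control v experimental.

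Power of the arm comparison:

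| Truncated | Complete data | As recorded | Completed only | Ranked last |
|---|---|---|---|---|
| 1.5% v 0.6% | 76% | 75% | 75% | 76% |
| 7% v 3% | 77% | 69% | 72% | 76% |
| 22% v 11% | 77% | 54% | 63% | 70% |
| 21% v 11%, late | 79% | 75% | 63% | 71% |

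Repeat runs of the same set-up differed by up to about 3 percentage points.

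Correlation of motion total with GRS (an analysis that 8.1 does not state; GRS noise SD 0.8):

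| Truncated | Complete data | As recorded | Completed only | Ranked last |
|---|---|---|---|---|
| 1.5% v 0.6% | 0.76 | 0.75 | 0.76 | 0.75 |
| 7% v 3% | 0.76 | 0.70 | 0.74 | 0.74 |
| 21% v 11% | 0.76 | 0.59 | 0.73 | 0.70 |
| 21% v 11%, late | 0.76 | 0.72 | 0.73 | 0.70 |
| 25% v 13%, unrelated to skill | 0.76 | 0.63 | 0.75 | 0.53 |

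With truncation unrelated to skill at 25% v 13% and no true difference between arms, false-positive rates in the same column order are 4%, 9%, 5% and 12%. In a separate set-up with 20% truncated in both arms at random, the rate stayed near 5%. Unequal rates, not truncation as such, raise false positives.

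**4. Dependence on sensor noise.** Skill variance over both arms is 1 + 0.75²/4 = 1.14 (SD 1.068), so the signal SD is 0.4 × 1.068 = 0.427. With noise SD 0.1, the total correlates 0.427/√(0.427² + 0.1²) = 0.97 with true skill, which presumes a very good sensor. With noise SD 0.6 it is 0.427/√(0.427² + 0.6²) = 0.58, and the GRS correlation at 21% v 11% then goes from 0.44 to 0.34. The direction persists; the absolute figures do not.

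**5. Illustration for the GRS.** Suppose knowledge of the arm shifts the GRS by d SD with no true difference. By normal approximation, k = d√(n/2) and the false-positive rate is Φ(k − 1.96) + Φ(−k − 1.96). For d = 0.3 and n = 30 per arm, k = 1.162 and the rate is 21%. Simulated Mann-Whitney rates for shifts of 0.1, 0.2 and 0.3 SD are 6%, 11% and 19% with 30 per arm, and 5%, 8% and 12% with 15 per arm.

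**The case against.** - **The protocol speaks of interrupting, not taking over.** This stands. Takeover is an inference. Early stopping is at least as natural a reading, since the consultant has by then finished the procedure and demonstrated the examination. An interruption followed by resumption could raise the total. A reader might infer that the theatre totals will be biased in a known direction; the text does not support that.
- **Incomplete cases might be recovered later.** This stands in part. The consultant also wears sensors, procedure-based assessments are listed for theatre, and the case report form is not among the documents. It would be too strong to say such cases could never be identified. But no such use is planned, and completion status is most reliable when noted at the time.
- **The illustrated analyses are not all in the plan.** This stands. Section 8.1 states no sensor–GRS correlation and no GRS comparison between arms.
- **The large losses need common, early truncation.** This stands. If truncation is rare or late, little is lost.
- **Every handling rule has a weakness.** This stands. Completed-only drops the weakest trainees and does worse than as-recorded when truncation is late (63% v 75% power). Ranking last replaces the sensor reading with the consultant's decision and fails when truncation is unrelated to skill (0.53 v 0.63).
- **The motion analysis is already blinded.** True, but this does not reach the consultant's conduct in theatre or the GRS. A reader might infer that the consultant knows the allocation; the documents say only that nothing prevents it.

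**Conclusion.** The concern holds as a gap in recording, analysis and masking. As written, a truncated total would enter the analysis as if complete and point towards skill, with no completion status specified to reveal it. The existing benchmark and blinding address other problems.

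The size cannot be known from the documents. Under the assumptions shown, the effect runs from negligible (76% to 75% power at 1.5% v 0.6%) to serious (77% to 54% at 22% v 11% with an early cut-off). Those figures rest on assumed truncation rates, an assumed cut-off and low sensor noise, and model truncation only. The GRS figures likewise assume both the rater shift and the comparison.

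The documents do not support the stronger conclusions that the theatre results are already invalid, or that one arm is certain to be favoured. The change is worth making because it is cheap, bears on the primary objective, and would itself show whether incomplete cases are rare.

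**What to change.** 1. **Section 7.6.** At the time of each theatre case, record whether the diagnostic arthroscopy was completed by the trainee, completed after an interruption, stopped early or taken over, and roughly when.
2. **Section 8.1.** Do not treat truncated totals as complete. Report the number of incomplete cases by arm, state one handling rule before the data are seen, and give as-recorded results as a sensitivity analysis. No particular rule is prescribed here; the investigators should choose one and give the reason.
3. **Sections 7.4 and 7.6.** Name the GRS rater. Do not tell the supervising consultant or the rater the allocation until the GRS is filed, and ask participants not to disclose it.

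The cost is a tick-box and short note per case, a few sentences in 8.1, and an instruction to participants and consultants. Masking may sometimes be broken. The consultant's discretion to intervene is unchanged.

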7.7. Discontinuation/Withdrawal of Participants from Study

Each participant has the right to withdraw from the study at any time. In addition, the Investigator may discontinue a participant from the study at any time if the Investigator considers it necessary for any reason including:

- Ineligibility (either arising during the study or retrospectively having been overlooked at screening)
- Significant protocol deviation
- Significant non-compliance with treatment regimen or study requirements
- Withdrawal of Consent
- Loss to follow up
- Exclusion from core or higher surgical training programme

The reason for withdrawal, if disclosed, will be recorded in the Case Report Form.

7.8. Definition of End of Study

The CUREC-approved 'Simulation-Based Arthroscopic Surgery Programme' will allow the repeated practice of technical tasks in a safe environment, whilst posing no risk to patient or learner. Our aim is to assess the effectiveness of simulation based arthroscopic training and to see whether it may have a role in surgical training. More specifically, we will assess the usefulness to training of the new elbow-attached motion sensors during routine, consultant-supervised procedures in theatre.

This research programme will take place over a five year period in the "Oxford Orthopaedic Simulation & Education Centre" which is situated within the Nuffield Department of Orthopaedics, Rheumatology and Musculoskeletal Science. This period expires in 2019.

8. STATISTICS AND ANALYSIS

8.1. Description of Statistical Methods

Motion analysis data from the elbow-worn wireless motion sensors produces similar data to the wired sensors our group has used previously.

Number of movements and path length are common to both devices. Data distributions will be assessed for normality. Previous studies show such data are not normally distributed and we would expect to use non-parametric tests, in this case the Mann-Whitney U test or Kruskal-Wallis test, to compare performance between groups during a given task. Mann-Whitney U tests will also be used within a group to compare performance before and after training on a simulator.

Surgical logbook data will be assessed using descriptive statistics, and motion analysis performance will be reported with reference to surgical experience.

Questionnaire data regarding the trainee and consultant perception of the utility of these sensors will be reported as descriptive statistics.

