4. OBJECTIVES AND OUTCOME MEASURES

Objectives	Outcome Measures	Timepoint(s) of evaluation of this outcome measure (if applicable)

Primary Objective Assess the usefulness of the new elbow-attached motion sensors during diagnostic knee arthroscopy as part of routine, consultant-
	
Motion analysis parameters during consultant-supervised diagnostic knee arthroscopy
 
Global rating scale during consultant-supervised diagnostic
	
At 3 months follow up, as part of and during the CUREC-approved 'Simulation-based Arthroscopic Surgery Programme' MSD-IDREC-2014-152

supervised training in theatre	knee arthroscopy	
Secondary Objective Assess the usefulness to training of the new elbow-attached motion sensors during simulated arthroscopy in the skills lab	Motion analysis parameters during simulated arthroscopy in the Skills lab	At baseline and after 3 months,

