5. STUDY DESIGN

The ‘Simulation-based Arthroscopic Surgery Programme’ MSD-IDREC-2014-152 is a CUREC-approved series of studies investigating the effect of new training methods for our future surgeons and using simulators, cadaver specimens and virtual reality models. These studies involve the assessment of trainee groups (including junior surgical trainees, specialist registrars and consultants) in two ways:

- 1 – on simulators, using metrics such as motion analysis data, global rating scales and participant feedback
- 2 – in theatre, using metrics such as global rating scales, procedure based assessments and participant feedback.

In this particular sub-study, we are recruiting up to 60 junior surgical trainees in T&O posts as part of their training programme. These will all undergo a baseline assessment on an arthroscopic simulator, after which they will be randomised 50:50 to either a control group (regular training i.e. their T&O post) or an experimental group (additional simulation training approx.. 1 hour per week) for the next three months. At 3 months they will undergo repeat assessment on the arthroscopic simulator, and in theatre.

Participants will use simple elbow-worn wireless motion sensors during simulation assessments and simulation training, and during usual training in theatre under consultant-supervision, while the patients received their normal treatment, to assess their effectiveness at monitoring learning and performance in addition to the usual forms of educational monitoring above. Over the course of the study, surgical logbook/training data will be collected by the participant and linked to their other results anonymously.

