7. STUDY PROCEDURES

7.1. Recruitment

The 'Simulation-based Arthroscopic Surgery Programme' MSD-IDREC-2014-152 recruits junior surgical trainees, specialist registrars, and their supervising consultants from the Oxford Deanery for simulation training using simple elbow-worn wireless motion sensors. Recruitment takes place using emailed adverts sent via clinical and academic departments e.g. newsletters. In this particular sub-study, we are recruiting up to 60 junior surgical trainees in T&O posts as part of their training programme. Those who express an interest to the invite circulated by the Deanery/Trust will be provided with a participant information sheet and have the opportunity to discuss this with an investigator. Those wishing to proceed will be invited to attend a baseline session where eligibility and consent are confirmed in person after the participant has the opportunity to ask any further questions regarding the study or participant information sheet.

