7.3. Baseline assessment

The first session will be a baseline meeting where eligibility and consent are confirmed once the participants questions regarding the previously provided information sheet are answered. Baseline simulator performance data using motion analysis will be gathered, plus some basis demographic data and information about surgical experience. They will also be asked to keep a note of all surgical procedures they perform in the coming 3 months. They will also be randomised to the control (usual training) or experimental (additional simulation training) group. This meeting will take about 45-60 minutes.

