7.4. Randomisation

At the first meeting after their baseline simulation assessment, they will be randomised by sealed envelopes method to either control or experimental groups. As the participant will be attending simulation training, they cannot be blinded to this, but they will be provided with a unique identifier for use during the motion capture which will allow the data to be recorded anonymously and analysed blindly as to the randomisation.

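### The 3-month simulator comparison of the randomised arms has no planned adjustment for the simulator baseline that every trainee provides; rank ANCOVA would use it at almost no cost

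*Combined protocol and SAP*

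**What the plan says.** The design supplies a same-metric baseline for the secondary outcome:

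- Section 5: "These will all undergo a baseline assessment on an arthroscopic simulator, after which they will be randomised 50:50". Section 7.4 confirms that the baseline comes before the envelopes are opened.
- Section 7.3: "Baseline simulator performance data using motion analysis will be gathered".
- Section 7.6: at 3 months "all participants will repeat a simulated arthroscopy assessment lasting about 30-45 mins, similar to that which occurred at baseline".
- Section 4 lists "Motion analysis parameters during simulated arthroscopy in the Skills lab" as the secondary outcome, at baseline and after 3 months.

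The analysis is in section 8.1. After a normality check, the investigators expect to use "non-parametric tests, in this case the Mann-Whitney U test or Kruskal-Wallis test, to compare performance between groups during a given task". The baseline appears once: "Mann-Whitney U tests will also be used within a group to compare performance before and after training on a simulator". Section 7.4 adds that the motion data will be "analysed blindly as to the randomisation".

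Two other items could be mistaken for adjustment. Section 8.1 reports motion performance in relation to surgical experience, but that is description. Section 7.6 benchmarks the trainee against the supervising consultant, but that applies in theatre and corrects for the case, not for the trainee's starting level. No section plans ANCOVA, a between-arm comparison of change, or any other baseline-adjusted comparison of the arms.

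**The concern.** A before/after test inside one arm mixes the training effect with ordinary learning over three months in post and with familiarity with the simulator. Only the contrast between arms isolates the randomised training, and the tests named for group comparisons ignore the baseline.

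If trainees who start better also finish better, part of the 3-month spread is predictable before randomisation. Leaving that part in the error term costs power, and a chance imbalance in starting skill goes uncorrected. This matters more in a small study: section 7.1 says "In this particular sub-study, we are recruiting up to 60 junior surgical trainees", and section 8.2 gives no power basis.

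The loss is efficiency only. Under randomisation the unadjusted Mann-Whitney test is valid. The theatre outcomes under the primary objective are measured only at 3 months, so they have no baseline of the same metric and the gain computed here does not apply to them.

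**Working it through.** **No figure to reproduce.** The documents give no alpha, power, effect size, SD or baseline-to-3-month correlation. The 60 is a recruitment ceiling.

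**Inputs.** From the documents: up to 60 trainees and 1:1 allocation, so at most 60 / 2 = 30 per arm. Assumed: two-sided 5%, a difference of 0.5 SD, and correlation ρ between baseline and 3 months of 0 to 0.7.

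**Step 1: variance removed.** Linear adjustment leaves a residual variance of 1 − ρ² times the unadjusted variance: 1.00 at ρ = 0, 1 − 0.09 = 0.91 at 0.3, 1 − 0.25 = 0.75 at 0.5, and 1 − 0.49 = 0.51 at 0.7.

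**Step 2: power, like for like on ranks.** Simulation used bivariate normal data; the rank results hold under any monotone rescaling, including a log. Mann-Whitney was asymptotic with continuity correction. For Quade's rank ANCOVA, rank both visits over all trainees, regress 3-month rank on baseline rank, and compare the residuals between arms.

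| ρ | Mann-Whitney | Rank ANCOVA | Rank ANCOVA type I error | Mann-Whitney n per arm to match |
|---|---|---|---|---|
| 0 | 45% | 45% | 5.0% | 30 |
| 0.3 | 45% | 48% | 4.9% | 32 |
| 0.5 | 45% | 55% | 5.0% | 38 |
| 0.7 | 45% | 71% | 5.0% | 54 |

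At ρ = 0.5 the adjustment is worth (38 − 30) × 2 = 16 extra trainees.

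**Step 3: what shrinks the gain** (30 per arm, 0.5 SD unless stated).

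- *Training weakens the correlation in the trained arm.* Control 0.5 and trained 0.2: 49% against 45%. Control 0.7 and trained 0.3: 56% against 45%. Type I error is 5.2% and 5.1%.
- *Algorithm drift.* Section 9.2 says the metric algorithms are refined as data accrue. If this added independent noise of 0.5 SD at each visit, total variance would be 1 + 0.25 = 1.25 and ρ = 0.5 would fall to 0.5 / 1.25 = 0.40. Power is then 43% against 38%: the gain halves from 10 to 5 points.
- *Both together.* Control 0.5 and trained 0.2 with noise: 40% against about 38%, a gain under 3 points. Control 0.7 and trained 0.3 with noise: 43% against 37%.
- *Larger effect.* At 0.8 SD the gain is about 3 points at ρ = 0.3 and 8 at 0.5. At 1.0 SD it is about 1 and 3.

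**Step 4: other sizes.** With 20 per arm and 0.5 SD, Mann-Whitney has 32% and rank ANCOVA 32 / 34 / 39 / 51% across the four correlations. If the 60 a year over 5 years in the synopsis were all randomised, that is 60 × 5 / 2 = 150 per arm. Mann-Whitney then already has 99% at 0.5 SD, so there is no useful gain; at 0.3 SD it has 72% against 72 / 75 / 83 / 93%.

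**Step 5: price if the baseline is useless.** At ρ = 0, rank ANCOVA power is unchanged. The log-scale 95% interval has half-width 0.519 SD adjusted against 0.514 unadjusted, and 0.519 / 0.514 = 1.01, about 1% wider.

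**The case against.** The arm comparison is inferred. Both objectives in section 4 concern the usefulness of the sensors, the synopsis calls the study observational, and no power target is set that could be missed. Section 8.1 states an expectation, speaks of groups in general and includes Kruskal-Wallis, so it may partly serve experience groups. On this view the more basic gap is that no arm comparison is specified, and adjustment is a refinement of it. The gain rests on a correlation that the documents do not give, which may be modest in a narrow band of junior trainees. Nor does any section commit to reprocessing the baseline data with a later algorithm.

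Much of this stands as a limit. The size is conditional: at a control-arm correlation of 0.5 and an effect of 0.5 SD, roughly 3 to 10 points is a fair summary once noise and unequal correlations are allowed for. Change scores or a stratified rank test would also use the baseline, and they were not compared here.

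It does not defeat the point. Randomising 50:50 to control or additional training, planning to analyse blind to allocation, and the aim in section 7.8 of assessing whether simulation training works make an arm comparison the natural reading. If the arms are compared, adjustment showed no loss of power at zero correlation. Section 9.2 says metrics are produced on request from raw data, so a single-version query looks feasible.

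**Conclusion.** The concern holds. No section plans a baseline-adjusted comparison of the randomised arms on the 3-month simulator metrics, although the same metric is collected from every trainee before randomisation. The planned tests are not wrong; they leave available information unused.

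With 30 per arm and a 0.5 SD difference, the gain in power is nil at correlation 0, about 3 points at 0.3, 10 at 0.5 and 26 at 0.7. It is smaller with drift noise, a weaker correlation in the trained arm, or a large effect. Correlation, effect size and alpha are all assumptions. The conclusion is limited to the secondary simulator outcome, and to an arm comparison that the design implies but no objective names. The change is worth making because the downside is negligible, not because a large gain is assured.

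**What to change.** Add to section 8.1:

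> The randomised arms will be compared on each 3-month simulator motion metric by rank ANCOVA (Quade), adjusted for the baseline value of the same metric, with participants analysed as randomised. For positive metrics such as number of movements and path length, the baseline-adjusted ratio with 95% CI from log-scale ANCOVA will also be reported. Baseline and 3-month metrics will be generated with the same algorithm version. Within-arm before/after changes are descriptive.

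Rank ANCOVA is the governing test and the log-scale ratio is the supporting estimate. The rank test keeps the expected non-parametric approach, needs no normality check to trigger it, and is unaffected by monotone rescaling, so it also suits smoothness. The log-scale interval does rest on its own model. No change is proposed for the theatre outcomes.

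The cost is this wording, one degree of freedom, and one query of the stored raw data with a single algorithm version, to be agreed with the collaborator that produces the algorithms. No new data are collected.
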